## Secondary Outcomes

- Weight (kg) From Consult up to 1 Year.
  - Weight change in kilograms assessed from medical chart review from consult up to 1 year
- Number of Participants With the Need for Supraglottoplasty Surgery (Escalation of Treatment) up to 1 Year.
  - The need for escalation of treatment with supraglottoplasty surgery will be assessed through medical chart review up to 1 year.

- Number of Participants With the Need for Acid Suppression Therapy Medication (Famotidine) From Speech Language Therapy Alone Group From the Day After the Consult up to the 3 Month Follow up Appointment.
  - The speech language therapy alone group will be assessed for the need for a prescription for acid suppression therapy (famotidine) from the day after the consult up to 1 year.
- Number of Participants With Each Type of Laryngomalacia (Types 1-3) Found on the Flexible Laryngoscopy Procedure at the Consult.
  - All patients will be scoped with a flexible laryngoscopy at the initial consult and the type of laryngomalacia (Types 1-3) will be noted.
- Number of Participants With the Need for a Different Acid Suppression Therapy Medication (Other Than Famotidine) From the Day After the Consult up to the 3 Month Follow up Appointment.
  - Both groups will be assessed for the need for a different acid suppression therapy medication (other than famotidine) from the day after the consult up to the 3 month follow up appointment.

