These patients will then be re-evaluated at their follow up appointment in 1 to 4 months. The families will take the PASS and I-GERQ-R surveys again to determine LM severity. If Pepcid is discontinued due to intolerance of side effects, they will be kept in the study in the same arm. If the family opts out of the follow-up appointment or they do not need to follow-up in-person, families will take the post surveys via REDCap or by mail. A REDCap link will be sent along with a letter to the caregivers to the caregivers' email address on file. If the families do not fill out the surveys within 2 weeks, paper copies of the surveys along with a letter to the caregivers will be sent to the caregivers' home address on file. If the families do not return the paper copy or the electronic copy of the surveys, researchers will call the participants for a reminder and will ask if the family wants another paper copy or survey link. The family may also answer the survey questions over the phone.

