# Study Outcomes

## Primary Outcome

- Airway Symptom Score Change From Consult (Baseline) to 3 Month Follow-up Appointment.
  - This will be parent-reported and measured using the Pittsburgh Airway Symptom Score (PASS) questionnaire. The PASS is a scale from 0-10 with a higher score indicating a worse outcome. This outcome will be assessed at the consult and the 3 month follow-up appointment.
- Infant Gastroesophageal Reflux Questionnaire (I-GERQ-R) Score Change From Consult (Baseline) to 3 Month Follow-up Appointment.
  - This will be parent-reported. There are 12 questions on the surveys on a scale of 0-42. A higher score indicates a worse outcome. Those with a score of  $\geq 16$  on this survey at the initial consult are excluded from the study, indicating true gastroesophageal reflux disease (GERD). This outcome will be assessed at the consult and the 3 month follow-up appointment.
- Change in Incidence of Airway Symptoms From Consult up to 1 Year Assessed Via Electronic Medical Chart Review.
  - Change in incidence of airway symptoms from consult up to 1 year assessed via electronic medical chart review. Notes from the Department of Otolaryngology will be reviewed which include reported symptoms from caregivers and symptoms seen upon exam. Airway symptoms included periods of apnea, chest wall retractions, cyanosis, stridor, noisy breathing, and increased respiratory rate.
- Change in Incidence of Dysphagia Symptoms From Consult up to 1 Year Assessed Via Electronic Medical Chart.
  - Change in incidence of dysphagia symptoms from consult up to 1 year assessed via electronic medical chart review. Notes from the Department of Otolaryngology will be reviewed which include reported symptoms from caregivers and symptoms seen upon exam. Dysphagia symptoms included choking, coughing, gagging with feeds and/or emesis after feeds.

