## **Analyses**

Stata/SE 16.1 will be used for all statistical analysis.  
P value < .05 will be used for statistical significance.

Baseline characteristics will be compared between AST and no-AST groups using Chi-squared or Fisher's exact test for categorical data and t-test (normally distributed) or Wilcoxon rank-sum (not normally distributed) for continuous data. Primary outcome measures will be change in LASS and I-GERQ-R scores from initial visit to follow-up and change in airway and dysphagia symptoms assessed by chart review during the 1 year following the initial visit. The LASS and I-GERQ-R scores will be compared between initial and follow-up surveys using Wilcoxon signed-rank tests. Change scores (post-pre) will be calculated for LASS and I-GERQ-R, and differences in the improvement in scores based on laryngomalacia severity or randomization group will be evaluated using Wilcoxon rank-sum tests. Associations between LASS or I-GERQ-R and time between initial and follow-up surveys will be evaluated using Spearman rank correlation. Symptoms and weight at initial and follow-up visits will be compared using McNemar's and Wilcoxon signed-rank tests, respectively. Change in weight percentile based on laryngomalacia severity or randomization group will be evaluated using Wilcoxon rank-sum tests.

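### The weight outcome has no fixed measurement time or rule for choosing among chart weights, and no weight analysis accounts for elapsed time

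*Combined protocol and SAP*

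**What the plan says.** Secondary Outcomes lists the outcome as "Weight (kg) From Consult up to 1 Year" and explains it as "Weight change in kilograms assessed from medical chart review from consult up to 1 year". Neither line says which weight in that year is the second measurement.

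The Analyses section has two sentences on weight. The first is a within-infant comparison: "Symptoms and weight at initial and follow-up visits will be compared using McNemar's and Wilcoxon signed-rank tests, respectively". The second compares groups, on a different scale: "Change in weight percentile based on laryngomalacia severity or randomization group will be evaluated using Wilcoxon rank-sum tests". Neither sentence gives a time point, and no growth reference is named for the percentile.

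Three other statements bear on timing:
- Methods, on the clinic follow-up: "These patients will then be re-evaluated at their follow up appointment in 1 to 4 months".
- Primary Outcome, on the questionnaires: "This outcome will be assessed at the consult and the 3 month follow-up appointment".
- Analyses, on symptoms, which share a sentence with weight: "change in airway and dysphagia symptoms assessed by chart review during the 1 year following the initial visit".

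The Analyses section plans a Spearman correlation with the interval between assessments for the two questionnaire scores. Weight has no counterpart.

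**The concern.** Weight is the one growth measure among the outcomes. An analyst following the plan could take the weight at the 1 to 4 month appointment, the last weight within the year, or the weight nearest 12 months. Each would comply, and the choice could be made after the data are seen.

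Whichever is taken, infants will have been growing for different lengths of time. On the kilogram scale in which the outcome is defined, that difference enters the result directly: it adds variation unrelated to treatment, and if the arms happened to be weighed at different average times it would produce a difference that is not a treatment effect. The authors evidently expected variable intervals, since they examine them for the questionnaires, but weight is the measure for which the interval matters most.

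**Working it through.** **The plan's own figure.** There is none for weight. The Sample Size Calculation gives 62 per group for airway symptom improvement; 62/80 = 0.775, so enrolling 80 per group allows for 22.5% attrition. I use 62 per arm only as a plausible analysed number.

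**Reading the sections together.** Secondary Outcomes: chart weights, up to 1 year. Analyses: initial and follow-up visits, undated. Methods: an appointment at 1 to 4 months. Nothing says which of these governs weight, and none fixes a single time.

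**How much spread timing alone adds (kilograms).** Assumptions, none from the documents: constant growth of g kg per month, and weighing times uniform between a and b months.
- SD of weighing time = (b − a)/√12. For 1 to 4 months: 3/3.464 = 0.866. For 1 to 12 months: 11/3.464 = 3.175.
- SD added to weight gain = g × that. At g = 0.3, 0.5, 0.7: 0.26, 0.43, 0.61 kg over 1 to 4 months; 0.95, 1.59, 2.22 kg over 1 to 12 months.
- The longest interval gives 4/1 = 4 times, or 12/1 = 12 times, the growing time of the shortest.

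**What that does to power (kilograms).** Further assumptions: true arm difference 0.3 kg; SD of gain at a fixed time 0.5 kg, both held constant over time so that only the mixing of times has an effect. Power ≈ Φ(0.3/(SD × √(2/62)) − 1.96), with √(2/62) = 0.1796.
- One fixed time: 0.3/(0.5 × 0.1796) = 3.34, power 0.92.
- 1 to 4 months, g = 0.5: SD = √(0.5² + 0.433²) = 0.66, power 0.71.
- 1 to 12 months, g = 0.5: SD = √(0.5² + 1.588²) = 1.66, power 0.17.

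| SD at fixed time | Fixed time | 1 to 4 months (g = 0.3 / 0.5 / 0.7) | 1 to 12 months (g = 0.3 / 0.5 / 0.7) |
|---|---|---|---|
| 0.4 kg | 0.99 | 0.94 / 0.81 / 0.63 | 0.37 / 0.17 / 0.11 |
| 0.5 kg | 0.92 | 0.84 / 0.71 / 0.57 | 0.34 / 0.17 / 0.11 |
| 0.6 kg | 0.80 | 0.72 / 0.62 / 0.50 | 0.32 / 0.16 / 0.11 |

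**Simulation with slowing growth (kilograms).** Rank-sum test, 62 per arm, 2000 replicates. Assumed growth is 0.4 to 0.8 kg per month to month 4 and 0.25 to 0.45 after; SD is 0.5 kg at 3 months, rising with the square root of time; the arm difference is 0.265 kg at every time. Ranges cover the growth rates and repeat runs.
- All at 3 months: 80 to 82%. Spread over 1 to 4 months: 38 to 72%. Spread over 1 to 12 months: 10 to 24%.
- Part of that fall is later measurement, not mixing: with every infant weighed at exactly 6.5 months power is about 49%, and at exactly 12 months about 30%.
- If the difference instead grows in proportion to gain, 1 to 12 months gives 27 to 53%.
- With no true effect but one arm weighed half a month later on average, the test rejects in 44 to 71% of trials over 1 to 4 months and 9 to 12% over 1 to 12 months. At 0.4 to 0.8 kg per month, half a month is 0.2 to 0.4 kg.

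**The test the plan does contain (percentile change).** Assumed: age-specific percentiles, baseline z-score mean −0.3 and SD 1, SD of z change 0.5, effect 0.3 SD at month 3. Power with all weights at 3 months is about 85%.
- Effect persists: 81 to 85% over 1 to 12 months, so little or no loss.
- Effect constant to month 3: about 83% over 1 to 4 months.
- Effect builds to month 3, then fades to zero by month 12: about 64% over 1 to 4 months and 37% over 1 to 12 months (mean differences 6.0 and 4.2 percentile points, against 8.0 at a fixed 3 months).

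**The case against.** The best defence is that there is only one window. Weight shares its Analyses sentence with symptoms, which are taken from the chart over 1 year, and Secondary Outcomes takes weight from the chart over the same year. The word for visits is plural and is not tied to the 1 to 4 month appointment. This stands as far as it goes: a reader might infer that the plan contradicts itself, 1 year in one section and 1 to 4 months in another, but the documents do not establish that. What remains is that even a single one-year window does not say which weight counts.

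A reader might also infer that the two descriptions analyse different infants, because Methods provides that "If the family opts out of the follow-up appointment or they do not need to follow-up in-person, families will take the post surveys via REDCap" and only surveys are collected that way. That rests on the same unproven link. The named source is the medical chart, so an infant followed remotely may still have a usable weight.

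The defence can add that the planned between-arm test uses percentile change. This also stands in large part. If the percentiles are age-specific, which is not stated, average growth is removed and mixed timing costs power only when the treatment effect changes over time. It does not repair the kilogram outcome as defined, nor does the within-infant signed-rank test, which says nothing about treatment because infants gain weight anyway.

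Finally, nothing in the documents suggests that the arms return at different times; one schedule applies to both. The half-month shift shows sensitivity and does not predict what will happen.

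**Conclusion.** The point holds as an unreconciled ambiguity with a practical consequence. The second weight has no fixed time or selection rule, and no weight analysis uses elapsed time although the questionnaires get such a check. Kilogram change reported as defined would largely reflect weighing time.

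The kilogram power and false-positive figures illustrate that outcome under assumed growth rates, SDs and timing; the documents give none of these. They are not the operating characteristics of the planned percentile test. For that test the loss runs from almost nothing to a fall from about 85% to 37%, depending wholly on how the effect changes with time.

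Since the stated hypothesis is no difference, a reader might conclude that the design is tilted toward confirming it. The documents do not support that as a general claim: a persistent effect on the percentile scale is hardly diluted, and unequal timing on the kilogram scale could produce a false difference instead.

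Weight is a secondary outcome, so the sample size and primary outcomes are unaffected. The change should be made, but the trial does not depend on it.

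**What to change.** Use the same definition in Secondary Outcomes and Analyses:
- Name one time point with a window and a selection rule, for example the dated chart weight, from any source, nearest 3 months after consult. A weight nearest 12 months may be reported separately, noting that power is likely to be lower there if the difference does not grow. Do not pool weights from different times into one change.
- Compare arms on age- and sex-standardised weight with a named growth reference, adjusted for baseline weight and actual days from consult to weighing.
- Report by arm the number of infants with a weight inside the window.

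The cost is plan wording and the abstraction of dated weights from charts already being reviewed. Some infants will have no weight in the window, and with no imputation planned the analysed number falls slightly.

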## Sample Size Calculation

Based on data from Dang et al [1], 62 participants per group will be needed to address the hypothesis that there is no difference in airway symptom improvement between AST and no-AST groups with alpha=.05 and power=.80 (two-tailed Fisher's exact test, G\*Power 3.1). Target enrollment will be 160 participants (80 in the AST group and 80 in the no-AST group, with 40 with mild laryngomalacia and 40 with moderate laryngomalacia in each group) to account for attrition.

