## Study Objectives

Purpose: To determine the outcome differences in patients 6 months and younger with laryngomalacia and dysphagia who are evaluated by speech language therapy (SLP) alone versus those with both SLP evaluation and acid suppression therapy (AST)

Hypothesis: We hypothesize that there will be no differences in outcomes between those that had SLP alone versus those that had both SLP and AST.

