### **Cross-Over**

Intent-to-treat analysis will be performed.

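### The analysis plan omits the between-arm symptom comparison used to size the trial, and 80% power to detect a difference cannot support the expected finding of none

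*Combined protocol and SAP*

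**What the plan says.** The Study Objectives section gives the expected result: "We hypothesize that there will be no differences in outcomes between those that had SLP alone versus those that had both SLP and AST". The Sample Size Calculation ties the trial's size to that statement for one outcome. It says 62 participants per group are "needed to address the hypothesis that there is no difference in airway symptom improvement between AST and no-AST groups", at alpha .05 and power .80, using a "two-tailed Fisher's exact test". It cites an earlier study as the source but prints neither the two improvement rates nor the difference between them. Enrolment is raised to 80 per group for attrition.

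The Primary Outcome section lists four outcomes: change in the airway symptom score (PASS, called LASS in the Analyses section), change in I-GERQ-R, and two from chart review, airway symptoms and dysphagia symptoms. The Analyses section confirms the last two as "change in airway and dysphagia symptoms assessed by chart review during the 1 year following the initial visit".

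The tests in the Analyses section are:

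- **Score changes:** "differences in the improvement in scores based on laryngomalacia severity or randomization group will be evaluated using Wilcoxon rank-sum tests". This is a between-arm test.
- **Symptoms:** "Symptoms and weight at initial and follow-up visits will be compared using McNemar's and Wilcoxon signed-rank tests, respectively". This compares visits, not arms.
- **Weight percentile change** (weight is a secondary outcome): rank-sum test by severity or randomization group.
- **Fisher's exact test:** named only for baseline characteristics.

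The decision criterion is p < .05. No between-arm effect estimate or confidence interval is mentioned for any outcome. The Cross-Over section adds "Intent-to-treat analysis will be performed".

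**The concern.** The Scientific Background section asks whether infants improve because of acid suppression or because laryngomalacia resolves by itself, and says the study would help establish guidelines. Only a comparison of the randomized arms can answer that. A before-after test will show improvement under either explanation, so the plan as written leaves the question open for two of its four primary outcomes.

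The sizing statement adds a second problem. A two-tailed Fisher calculation gives the chance of rejecting equality when a particular difference exists. It says nothing about the chance of supporting equality. The trial expects a non-significant result, and without an interval that result cannot be told apart from imprecision. If it were read as no difference, a guideline could rest on a trial that was unlikely to detect a modest effect.

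**Working it through.** **1. Test assigned to each primary outcome**

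| Primary outcome | Between-arm test in Analyses | Between-arm test elsewhere | Between-arm interval |
|---|---|---|---|
| PASS/LASS change | rank-sum | – | none |
| I-GERQ-R change | rank-sum | – | none |
| Airway symptoms (chart) | none | Fisher's, in the Sample Size Calculation only | none |
| Dysphagia symptoms (chart) | none | none | none |

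**2. What McNemar's test shows.** It uses each patient's change between visits. Run pooled, it ignores the arm. Run within each arm, it gives two before-after results and no comparison. Illustration with assumed counts, all patients symptomatic at baseline: symptoms resolve in 45/62 in one arm and 28/62 in the other. With no changes in the opposite direction, the exact McNemar p is 2 × 0.5^45 in one arm and 2 × 0.5^28 in the other, both far below .001. The between-arm Fisher p is .003. The plan would report improvement in both arms and never test the 27-point difference (72.6% − 45.2%).

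**3. The plan's figure of 62.** It cannot be reproduced, because the rates are not printed. The calculation was therefore inverted. All pairs of binomial counts were enumerated at n = 62 per arm, with exact two-sided Fisher p < .05, and the upper rate giving 80% power was found for each assumed lower rate:

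| Lower rate (assumed) | Upper rate for 80% power | Difference |
|---|---|---|
| .05 | .232 | .182 |
| .10 | .314 | .214 |
| .20 | .447 | .247 |
| .40 | .658 | .258 |
| .50 | .755 | .255 |
| .60 | .837 | .237 |
| .70 | .909 | .209 |
| .80 | .968 | .168 |
| .85 | .991 | .141 |

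The range is about 14 to 26 points. At 80 per arm with no attrition it is about 13 to 23 points. The step from 62 to 80 allows 1 − 62/80 = 22.5% attrition.

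**4. Chance of a non-significant result when the true difference is 10 points.** For lower-arm rates of .05 to .85 it is .657 to .835 at 62 per arm and .519 to .808 at 80 per arm. The low end occurs only at extreme rates (5% vs 15%, 85% vs 95%). For lower-arm rates of 20% to 70%, it is .81 to .84 at 62 per arm.

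**5. Interval width with equal true rates p (assumed).** Half-width = 1.96 × √(2p(1−p)/n).

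| p | n = 62 | n = 80 |
|---|---|---|
| .9 | .106 | .093 |
| .7 | .161 | .142 |
| .5 | .176 | .155 |

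For score changes the half-width is 1.96 × √(2/62) = 0.35 SD. The documents give no SD.

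**6. What a p-value alone hides (assumed counts).** If 43/62 and 37/62 improve, the difference is 9.7 points and Fisher p = .35. The Newcombe 95% CI runs from −7 to +26 points, so the result is non-significant and still compatible with a large effect.

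**The case against.** Five points can be made for the plan.

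- **It is one combined document, and the airway Fisher's test is named in it.** This is true, and for airway symptoms the gap may be an oversight. Dysphagia, though, has no between-arm test anywhere. The Analyses section mentions randomization group for scores and weight percentile but not for symptoms. A test named only in a power calculation also leaves the definition of improvement and the handling of visits open until data are seen. The intent-to-treat sentence says which arm a participant counts in; it names no test.
- **Addressing a hypothesis of no difference is ordinary wording for a statistical null.** On that reading the calculation is coherent. It still gives no power for the expectation in Study Objectives, and it does not affect the missing comparison or the missing intervals. It is also true that the documents never say a non-significant result will be read as equivalence. That part of the fix is a safeguard for a trial that expects such a result.
- **The planning rates may be in the cited study.** They may be, but they are not in this document, so the reader cannot tell what difference 62 was meant to detect. This is missing detail rather than an error.
- **The magnitudes rest on assumed rates and on a single improved/not-improved endpoint.** This stands. They show how little a non-significant result would exclude; the missing comparison needs no arithmetic.
- **Intervals beside the rank-sum tests are a lesser matter.** This also stands. Alone they would be a reporting improvement.

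**Conclusion.** The concern holds and should be fixed before analysis. Within the Analyses section, two of four primary outcomes have no randomized comparison, and none of the four has a between-arm interval. This rests on the text alone. The stated 80% is power to detect an unprinted difference, about 14 to 26 points at 62 per group if lower-arm improvement lies between 5% and 85%. A true 10-point difference would then be missed in 66% to 84% of trials. With equal rates of 90% to 50%, the 95% interval would extend about ±11 to ±18 points at 62 per group, or ±9 to ±16 at 80. All these rates are assumptions. Nothing here shows that 62 is the wrong number.

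**What to change.** **Sample Size Calculation.** State both assumed improvement rates and the difference that 62 per group has 80% power to detect. Do not present this as power for the no-difference hypothesis.

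**Analyses, symptom outcomes.** Define airway symptom improvement and dysphagia symptom improvement, including the time point within the year. Add an intent-to-treat between-arm comparison of each: Fisher's exact test plus the risk difference with a 95% CI. Say how this fits with the Analysis Inclusion and Missing Data sections, which restrict the analysis to eligible patients and rule out imputation. McNemar's test can stay as a description of change over time.

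**Analyses, score outcomes.** Beside the rank-sum tests for PASS/LASS and I-GERQ-R change, report the between-arm difference with a 95% CI, for example Hodges-Lehmann. Use one name for the airway score.

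**Interpretation.** State that a non-significant result will not by itself be read as no difference, and that the conclusion will rest on which differences the interval excludes.

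**Optional.** Prespecify an equivalence margin, at least for airway symptoms. This is not a wording change: it needs a clinical justification that the documents do not supply.

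**Cost.** Apart from the optional margin, the changes are wording, two comparisons and four intervals, all from data already planned for collection, with no extra patients. The power claim becomes less favourable, the dysphagia comparison adds a primary test, and the intervals may leave the result inconclusive.
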